Viral spread (for both outcomes)	Total lockdown Partial lockdown (geographical, step-wise/graduated response) Curfew School closure Closure of shopping malls, gyms, churches, parks Remote work Restrictions to national/subnational mobility Prohibition of mass gatherings
Health systems response (for COVID-19 deaths outcome)	Interventions to increase testing capacity Interventions to increase the number of ICU/critical beds
Mitigation strategies (for both outcomes)	Direct social assistance (in-kind/cash) Cash transfer Withdrawal of pension funds

Comparator

In an interrupted time series analysis, the comparator is a counterfactual outcome defined as the projection of the pre-intervention trend to simulate what would have happened if the policy had not occurred (see Statistical Analysis Plan for definitions).

Outcomes

We will assess three primary outcomes. The first outcome will be the 7-day moving average of daily confirmed cases of COVID-19/SARS-CoV-2. The second outcome is the time-varying reproductive number between the current and previous period.¹⁹ The third outcome is the 7-day moving average of the daily number of deaths by COVID-19 in Latin American subnational regions. For the statistical modelling, these averages will be rounded to the nearest integer. We will consider a 7-day lag as the primary lag. Details on sensitivity analyses can be found in the Statistical Analysis Plan.

We define the outcomes following the official national sources definitions, as each country applies its criteria to define the occurrences and the deaths caused by COVID-19. It is important to note that those criteria are not always clearly stated, but all subnational units are under the same measure at each time.

Data sources

We will obtain COVID-19 cases and deaths data, as well as the covariates, on official government sources, such as the Ministry of Health and Ministry of Science and Technology (see Supplementary Appendix Table S2). The intervention information will come from legal documents, official statements, and quantitative accounts from trustable sources.

Covariates

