#### *Outcome definitions*

The first outcome will be the 7-day moving average of daily confirmed cases of COVID-19/SARS-CoV-2. The second outcome is the time-varying reproductive number between the current and previous period. The third outcome is the 7-day moving average of the daily number of deaths by COVID-19 in Latin American subnational regions. For the statistical modelling, these averages will be rounded to the nearest integer. We will consider a 7-day lag as the primary lag. We will use the definition of COVID-19 case and death which is valid at any given time in each country.

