#### *Analysis methods*

The primary analysis will use interrupted time series (ITS) for each subnational unit to examine the causal effect of COVID-19 policies on primary outcomes. Interrupted time series is a widely used tool in causal inference that allows comparing trends before and after the introduction of an intervention. The counterfactual outcome is the projection of the trend in the period before the introduction of the intervention into the time period was introduced. The unit of analysis in this study is days, starting from the date of the first case.

The standard model for an ITS regression is as follows

$$(1) Y_t = \beta_0 + \beta_1 time_t + \beta_2 post_t + \beta_3 timepost_t + \beta'_4 X + \mu_t$$

where  $time_t$  is a variable which equals one at the first time point  $t$  and increases by one after each subsequent time point;  $post_t$  is a dummy variable that equals to zero prior to the introduction of the intervention ( $p$ ) and equals one for every time point thereafter;  $timepost_t$  is a variable that equals to zero until time  $p-1$ , and increases by one for each subsequent time point; and  $X$  is a vector of covariates. Coefficient  $\beta_3$  is the coefficient of interest and represents the change in slope after time  $p$ .

The validity of the ITS rests on three assumptions. Assumption 1 states that the expectation of the pre-intervention level and trends would be the same irrespective of whether the sample received the treatment. Assumption 2 states that in the absence of treatment, the outcome of interest would remain unchanged in the post-intervention period. Assumption 3 states that the time trends in the pre and post periods can be expressed as a linear combination of parameters.

Using the potential outcomes framework, the estimated effect of a policy at time  $p$  could be defined as

$$(2) \Delta_t = Y_t(1) - Y_t(0)$$

These difference could also be expressed in terms of two equations

$$(3) Y_t(1) = \alpha_0 + \alpha_1 time_t + \alpha_2 post_t + \alpha_3 timepost_t + \varepsilon_t$$

$$(4) Y_t(0) = \theta_0 + \theta_1 time_t + \theta_2 post_t + \theta_3 timepost_t + \nu_t$$

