Assumption 2. We will explicitly incorporate co-occurring interventions in a seven-day period as a combination of interventions. We will also adjust for changes in the case definition of COVID-19 cases and deaths for each of the respective outcomes. We will report in the Supplementary Appendix the exact dates considered in the analysis for each country/subnational unit and the interventions included in each intervention period.

Assumption 3. We will introduce flexible spline functions to account for seasonality and long-term trends. We will add a scale parameter, which will be the Pearson statistic divided by the residual degrees of freedom, to account for potential overdispersion (a violation of the Poisson regression assumption). We will test for autocorrelation using the Durbin-Watson tests and visual plots of the autocorrelation function and partial autocorrelation function. If there is evidence of autocorrelation, we will use the Newey-West method to obtain adjusted standard errors.

Therefore, in the final analysis, we will use Poisson regression to model the count data.. The final model is an extension of the regression described in equation 1 with the specifications described above. The model will include each of the interventions (either as single interventions or combinations of), denoted  $j = 1, \dots, J$ . This method allows estimating simultaneously the effect of several interventions. We will consider interventions implemented within a 7-day period as a combination of interventions, following previous studies. This means that the maximum number of combinations of interventions is 52,  $t = 1, \dots, 52$ . We will estimate the effect of the interventions separately when interventions are separated by at least seven consecutive days and for a maximum period of 30 days. The primary analysis will include a 7-day lag to account for the delay in the intervention to be effective, considering the incubation period of SARS-COV2.

$$(5) \ln(Y_t) = \beta_0 + \beta_{1j}time_{tj} + \beta_{2j}post_{tj} + \beta_{3j}timepost_{tj} + \mu_t$$

This model will be run at the municipal level and, therefore, we expect to run 10,000 regressions multiplied by the number of combinations of interventions at each municipal level. Coefficient  $\beta_{3j}$  is the coefficient of interest and represents the change in slope after the intervention  $j$  at period  $t$ .

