In coefficient of interest at a second stage, we will pool the effects for each intervention -or combination of interventions- (i.e. the coefficient of interest  $\beta_{3j}$  from the local level regression) using a random-effects meta-analysis. This meta-analysis will provide information to obtain a pooled effect estimate and a measure of heterogeneity. We will use the  $I^2$  as a measure of heterogeneity.

If the heterogeneity is moderate or high ( $I^2$  higher than 50%), we will carry out a meta-regression to assess whether subnational level determinants can explain the observed heterogeneity. We will analyse the following covariates: (i) Population size, (ii) Population density, (iii) Proportion of population over 60 years old, as a proxy for age structure of the population, (iv) Household density, and (iv) Proportion of population with basic education, as a proxy of socioeconomic status.

The meta-regression has the effect size  $\widehat{\theta}_k$  of a first-stage regression  $k$  as the outcome, covariates  $x_{ik}$ , a fixed effect  $\rho_1 S_a$  for the second-tier level  $a$  (i.e. State or Region) and a random-effect  $\delta_2 N_b$  for the national level  $b$  and a fixed effect  $\rho_2 Y$  for the time of the year (quarterly periods)(equation 6). The equation includes two types of independent errors, where  $\varepsilon_k$  is the sampling error of the effect size and  $\varsigma_k$  is the random-effect error term.

$$(6) \theta_k = \gamma_1 x_{1k} + \dots + \gamma_n x_{nk} + \rho_1 S_a + \delta_2 N_b + \rho_2 Y + \varepsilon_k + \varsigma_k$$

These controls for higher levels of administration and time of the year will allow us to control for constant characteristics at the subnational and national level, as well as changes in the effectiveness throughout the pandemic.

We will carry out the following sensitivity analyses: (1) comparison of effect estimates using a 5-day and 10-day lag; (2) quasi-myopic analyses to control for anticipatory effects (if there is evidence of), and (3) placebo tests evaluating changes at times when no policy was implemented. In the analyses for the number of cases and time-varying R, we will run additional sensitivity analyses estimating the number of SARS-CoV-2 cases corrected by under-ascertainment derived from mortality statistics.

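### For ICU-bed policies on deaths, the pooled slope change beta3 does not measure the benefit: a constant proportional saving is a step in beta2, which is fitted but never pooled

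*Protocol*

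**What the plan says.** Protocol, Methods, Interventions, Table 1 lists "Interventions to increase the number of ICU/critical beds" under Health systems response, a domain marked "for COVID-19 deaths outcome". The SAP (Outcome definitions) defines that outcome: "The third outcome is the 7-day moving average of the daily number of deaths by COVID-19". It does not say whether the average is trailing or centred.

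In SAP, Analysis methods, the model is log-linear: "in the final analysis, we will use Poisson regression to model the count data". Equation 5 holds a step term, post, which "is a dummy variable that equals to zero prior to the introduction of the intervention" and is one afterwards, and a slope term, timepost. For every intervention and outcome, beta3 "is the coefficient of interest and represents the change in slope after the intervention". At the second stage, "we will pool the effects for each intervention -or combination of interventions- (i.e. the coefficient of interest" is beta3 again. Beta2 is fitted but has no stated use.

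The Protocol (Statistical analysis) relies on the pooled result to say whether each intervention reduced cases and deaths. None of the listed sensitivity analyses (5- and 10-day lags, quasi-myopic, placebo, under-ascertainment) examines beta2.

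**The concern.** A policy on transmission changes the growth rate of the epidemic, so a change in slope is a natural summary. ICU beds act on fatality. Deaths are earlier infections times fatality, so a proportional cut in fatality lowers the whole death curve by a constant factor and leaves its growth rate alone. On the log scale that is a step.

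The SAP's own definition of the effect, Y(1) minus Y(0) in equation 2, includes the step: with theta2 and theta3 set to zero under Assumption 2, the contrast of equations 3 and 4 keeps both alpha2 and alpha3. The pooled quantity is therefore narrower than the defined effect. For ICU beds it can leave out all of it.

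At stake are the mortality conclusion for ICU-bed policies and the reading of I-squared. If beta3 mainly reflects when beds opened, differences in opening date between municipalities will show as heterogeneity and may trigger the meta-regression.

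**Working it through.** **Inputs from the documents.** Log link with step and slope terms (SAP equation 5); 7-day primary lag; effect period of at most 30 days; timepost equal to 1 on the first day after the break, so it runs from 1 to 30; 7-day moving average of deaths.

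**Assumed inputs.** The documents give no effect size, growth rate, pre-policy length or opening date. Assumed: 20% fewer deaths; underlying death trend -0.03, 0 or +0.03 per day; 30 or 60 pre-policy days; effect starting on day 0, 7, 14 or 22 after enforcement. Splines and rounding are not modelled. The plan states no figure to reproduce.

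**Step 1, algebra.** If deaths are multiplied by (1-s) from the break onward, then ln(Y) = beta0 + beta1 x time + ln(1-s) x post. Hence beta2 = ln(1-s) and beta3 = 0 at any growth rate. With s = 0.20, beta2 = ln 0.8 = -0.223 and beta3 = 0.000.

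**Step 2, noise-free Poisson fits of equation 5**, break at enforcement + 7 days, 30 days after it:

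| Effect starts (days after enforcement) | Series | beta3 per day |
|---|---|---|
| 7 | daily counts | 0.000 |
| 7 | trailing 7-day average | -0.003 to -0.005 |
| 0 | daily, trailing or centred | +0.0005 to +0.0065 |
| 14 | daily, trailing or centred | -0.007 to -0.011 |
| 22 | daily, trailing or centred | -0.009 to -0.011 |

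The upper value +0.0065 comes from 30 pre-policy days and a rising trend. With 60 pre-policy days and daily counts the range for onset on day 0 is +0.001 to +0.003.

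**Step 3, true benefit over the same window.** Onset on day 0 or 7 covers all 30 days: ratio 0.80. Onset on day 14 covers 23 of 30 days: exp(-0.223 x 23/30) = 0.84. Onset on day 22 covers 15 of 30: exp(-0.223 x 15/30) = 0.89. The later openings avert fewer deaths but give the more negative beta3.

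**Step 4, does noise hide this?** Simulation of 300 units with Poisson noise (20 deaths/day, growth 3% per day, 30 pre-policy days, 20% saving), pooled by DerSimonian-Laird; beta3 with 95% CI:
- step at the break, unsmoothed: -0.00003 (-0.0007 to 0.0006)
- step at the break, centred average: -0.0004 (-0.0010 to 0.0003)
- step at the break, trailing average: -0.0032 (-0.0038 to -0.0025)
- effect from enforcement, unsmoothed: +0.0066 (0.0060 to 0.0073)
- effect from enforcement, trailing average: +0.0041 (0.0034 to 0.0047)

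The same true saving is scored as null, beneficial or harmful, depending on timing and smoothing.

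**Step 5, the alternative.** The mean of timepost over 1 to 30 is (1 + 30)/2 = 15.5, so the average log ratio of fitted to projected deaths is beta2 + 15.5 x beta3. With days 0-6 left out, onset on day 0 gives 0.80 on daily counts or a trailing average and 0.81 to 0.85 on a centred one (upper end with 30 pre-policy days). Onset on day 7 gives 0.80 to 0.82. Onset on day 14 or 22 gives 0.84 to 0.92, against true averages of 0.84 and 0.89. If days 0-6 are kept, onset on day 0 contaminates the pre-trend and the ratio can reach 1.03.

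**The case against.** **Null or harmful is not the general result.** This stands. A reader might infer that a working ICU policy will always be scored as ineffective or harmful. The documents do not support that. They give no opening schedule or fatality reduction, and the planned outcome is smoothed. A trailing average, late opening or phased opening makes beta3 negative (phased opening over 14 or 30 days gave -0.005 to -0.010). A harmful sign needs an effect before the lagged break, or a fixed number of beds overtaken by epidemic growth, in which case the share saved is no longer constant. What remains is that the sign is set by timing and smoothing.

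**Ranking.** A reader might also infer that ICU policies will rank below transmission policies because of the coefficient. That does not follow. A policy that stops growth of 0.05 to 0.10 per day also looks larger on the average-ratio scale: exp(-0.05 x 15.5) = 0.46 and exp(-0.10 x 15.5) = 0.21, against 0.80 for the ICU example. The documents plan no ranking either.

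**The alternative depends on extrapolation.** This stands as a limitation. With no policy effect and mild deceleration (ln deaths = 0.03d - 0.0003d², d in days from enforcement), the average ratio is about 0.55 to 0.68. Beta3 is biased too (-0.02 to -0.03 per day). The SAP itself warns about non-linear epidemic curves.

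**Simplified model.** The fits omit splines and rounding, so the magnitudes are indicative. The algebra of step against slope in equation 5 does not depend on them.

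**Conclusion.** The point holds in a limited form. For ICU-bed policies on deaths, beta3 does not measure lives saved, and the term that carries a constant proportional saving is fitted but not pooled. With a 20% saving, beta3 ranges from about +0.0065 to -0.011 per day according to opening date, pre-policy length, trend and averaging. A working policy can be scored as having no effect or, if it acts before the break, as harmful, while later opening with fewer deaths averted looks better. Differences in opening date will also enter the heterogeneity estimate.

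This rests on the assumed saving, trends, pre-policy lengths and onset days. Only the algebraic result (beta2 = ln(1-s), beta3 = 0 for a step at the break) is free of them. It would be too strong to say that the mortality aim as a whole cannot be answered: the problem concerns one row of Table 1, and beta2 is available from every fit. The plan should be changed, but the defect does not invalidate the design.

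**What to change.** In SAP, Analysis methods, add a rule for the deaths outcome that applies to any intervention period containing an ICU-bed policy, alone or in a combination:

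- Fit equation 5 without days 0-6 after enforcement.
- Pool beta2 + 15.5 x beta3 (timepost 1 to 30), with its standard error from the joint covariance of the two coefficients, and report the exponential as the ratio of fitted to projected deaths over 30 days.
- Keep pooled beta3 as a secondary result.
- State whether the 7-day average is trailing or centred and how many pre-policy days are used, since both move the result.
- Read the ratio together with the planned splines and placebo tests, because it relies on the projected log trend.

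The cost is SAP wording, one refit per affected period and a somewhat wider interval from dropping seven days. No new data are needed.

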The first model at the local level does not include covariates (see below). The second model (i.e. the meta-analysis), we will examine the change in heterogeneity after adjusting for several covariates at the local level. Local level covariates include projected population size in 2020, demographic density, age-structure of the population, household density and socioeconomic status. We will use data from official sources of information, primarily the latest national population census in each included country.

Statistical analysis

The Statistical Analysis Plan provides details on the modelling assumptions. We will use an interrupted time series design, where each local government acts as its own control.^{20,21} The main

strength of this design is its capacity to distinguish the effect of the intervention from secular change.²² We will use a Poisson regression to model the count data (for both outcomes) and accounting for overdispersion and secular trends.²³ A full discussion on potential biases and violations of assumptions can be found in the Statistical Analysis Plan.

In a second stage, we will use random effects meta analysis to pool the effect estimates for each intervention or combination of interventions. This analysis informs whether any implemented intervention was effective to reduce COVID-19 cases and deaths and the degree of heterogeneity between the effects at the local level. If we observe high levels of heterogeneity (defined as higher than 50%), we will also use standard meta-regression techniques to assess whether local level determinants (see *Covariates*) can explain the observed heterogeneity.

We will build the models and test the analytical strategy using publicly available data on COVID-19 cases and deaths from Finland and Sweden from January 1 to March 31.

References

2. United Nations Department of Economic and Social Affairs. World Social Report 2020: Inequality in a rapidly changing world. New York, United States: United Nations; 2020.
3. World Health Organization. Report of the WHO-China Joint Mission on Coronavirus Disease 2019 (COVID-19)2020. <https://www.who.int/docs/default-source/coronaviruse/who-china-joint-mission-on-covid-19-final-report.pdf> (accessed March 26, 2020).

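### The heterogeneity measure for aim 3 has no stated reference model, and the only two models written down mix local covariates with state, country and quarter terms

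*Protocol*

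**What the plan says.** The Protocol's Covariates section sets the measure: in the meta-analysis stage, "we will examine the change in heterogeneity after adjusting for several covariates at the local level". The covariates it lists are population size, density, age structure, household density and socioeconomic status. Its Statistical analysis section asks whether local determinants "can explain the observed heterogeneity".

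The SAP (Analysis methods) describes two second-stage models.

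- **Random-effects meta-analysis of the slope-change coefficients.** "This meta-analysis will provide information to obtain a pooled effect estimate and a measure of heterogeneity". It has no covariates and no area or time terms.
- **Equation 6, fitted if I² exceeds 50%.** The stated purpose is to "carry out a meta-regression to assess whether subnational level determinants can explain the observed heterogeneity". In one step it enters the five covariates, a fixed effect for each state or region, a random effect for country and a fixed effect for quarter.

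The SAP treats the last three as adjustment, not as local determinants: "These controls for higher levels of administration and time of the year will allow us to control for constant characteristics". It specifies no covariates-only model, no model with the area and time terms alone, no order of entry and no partition of explained heterogeneity. The listed sensitivity analyses (lags, anticipation, placebo dates, under-ascertainment) do not supply one.

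**The concern.** The Protocol describes a change due to local covariates. The two models that the SAP writes differ by those covariates and by three sets of place and time terms. A fall in τ² or I² from the first model to the second therefore cannot be read as the contribution of population, density, age, crowding or education. State and quarter terms can absorb heterogeneity even when no local covariate matters. The SAP includes them because it expects stable differences between areas and changes in effectiveness over the pandemic, so the fall may well be more than trivial.

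What is at stake is the explained-heterogeneity summary for aim 3, and any policy reading of it.

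**Working it through.** The plan states no figure on this point, so there is none to reproduce. The check compares the models as written and then shows the size by simulation.

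**Algebra.** Write the true between-municipality variance as V = P + C + L, where P is the state, country and quarter part, C the part due to the covariates and L the rest. If the covariates vary only within states:

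- flat model: τ² ≈ P + C + L
- covariates only: τ² ≈ P + L
- state and quarter only: τ² ≈ C + L
- equation 6: τ² ≈ L

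The apparent share explained, 1 − τ²(adjusted)/τ²(reference), from flat to equation 6 is (P + C)/V. With C = 0 it equals P/V, although the covariates explain nothing.

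**Simulation inputs.** From the documents: 9 countries, five covariates, the structure of equation 6. Assumed: 1,000 municipal estimates, 10 states per country, 4 quarters, total true variance 1, sampling variances 0.3 to 0.9 (flat I² about 64%). Estimation was by method-of-moments meta-regression, with 40 replicates per row. State was fitted as fixed dummies and the country term omitted as redundant (see below). Percentages are means of the replicate ratios.

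| Assumed truth | τ² flat | τ² covariates only | τ² state + quarter | τ² equation 6 | Fall, flat to eq. 6 | Fall, flat to covariates only | Fall, state + quarter to eq. 6 (of what remains) |
|---|---|---|---|---|---|---|---|
| P 0%, C 0% | 0.981 | 0.981 | 0.980 | 0.981 | 0% | 0% | 0% |
| P 30%, C 0% | 0.978 | 0.977 | 0.696 | 0.696 | 29% | 0% | 0% |
| P 60%, C 0% | 0.988 | 0.989 | 0.396 | 0.397 | 60% | 0% | 0% |
| P 50%, C 10%, covariates within state | 0.980 | 0.880 | 0.504 | 0.402 | 59% | 10% | 20% |
| P 50%, C 10%, half of covariate variation between states | 0.972 | 0.853 | 0.456 | 0.403 | 58% | 12% | 12% |

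In the second row I² goes from 64% to 56%, and in the third from 64% to 42%. The third crosses the plan's own 50% mark with no covariate effect at all. In the fourth row the last step is (0.504 − 0.402)/0.980 = 10% of the total, which is the true share.

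**A different layout and estimator.** Assumed: 9 countries × 20 states × 12 municipalities, effect SD 0.05 per day, municipal SE about 0.03, null covariates, REML, 20 replicates.

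- 30% of variance at country and state level: 1 − 0.00170/0.00242 = 30%; I² 75% to 68%.
- 50%: 1 − 0.00123/0.00236 = 48%; I² 75% to 61%.
- 75%: 1 − 0.00062/0.00227 = 73%; I² 74% to 44%.

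In each case τ² with state and quarter terms alone equals that of equation 6, so the null covariates add 0%.

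**Between-state part of the covariates.** State terms also absorb any covariate variation that lies between states. With covariates assumed to explain 30% of heterogeneity, the step from state and quarter terms to equation 6 recovered about 15% of the total when half of the covariate variation lay between states, and about 6% when 80% did. Flat to covariates only recovered 30% to 32%.

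**Country term.** States are nested in countries, so state dummies already span country. The design matrix has rank 90 with or without country dummies. The REML log-likelihood with state dummies is −48.491197 at country variances of 0, 0.1, 1 and 10. The data carry no information on that variance.

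**The case against.** The strongest reply is that the plan never says the change will be taken from the flat model to equation 6. Read literally, the Protocol sentence compares a flat model with a flat model plus local covariates, and that step gives 0% under null covariates. The SAP also labels the area and time terms as controls, so a careful analyst need not credit them to local determinants. This stands: misattribution is a risk left open, not a stated intention.

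Three further points stand.

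- The SAP's question can also be answered from the γ coefficients in equation 6. These are adjusted for place and quarter and are not inflated.
- The simulated sizes rest on assumed variance shares, and the range starts at 0%.
- The redundant country term does not alter the covariate estimates, and the plan promises no country-level variance share.

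A reader might infer that the plan, followed as written, will report a large share as explained by local determinants that explain none of it. The documents do not support that, because they neither define the comparison nor give the variance shares. A reader might also conclude that local determinants should be credited only with the step from state and quarter terms to equation 6. That overcorrects, because it discards their between-state contribution.

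What the reply does not remove is the gap. The Protocol names a change in heterogeneity as a measure, the only adjusted model specified is equation 6, and the covariates-only model that the literal reading needs appears nowhere.

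**Conclusion.** The concern holds as an unspecified reference model. With the two models written, the only computable change mixes local covariates with place and time. If that change were reported as the effect of local covariates, the overstatement would be close to the share of heterogeneity at state, country and quarter level: about 0% if none lies there, and about 30% to 73% in simulations that assume 30% to 75% with null covariates. The true shares are unknown, so this is a range under assumptions, not a forecast.

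The effect is confined to the τ² and I² summary. The coefficients in equation 6, the pooled effects of aim 1 and the heterogeneity estimate of aim 2 are untouched. The country random effect is not identifiable beside state fixed effects; this is a specification error with little consequence for the covariate results. The point should be fixed, but it is not critical, because aim 3 is conditional on I² above 50% and exploratory.

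**What to change.** Prespecify four second-stage models, fitted to the same municipalities for each intervention or combination:

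- (0) flat random-effects meta-analysis
- (1) the five local covariates only
- (2) state and quarter terms only
- (3) both sets of terms

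Report the change in τ² and I² for three steps, each under its own label:

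- 0 to 1: local covariates, unadjusted for place and time
- 0 to 2: place and time
- 2 to 3: the within-state contribution of the covariates, given as a share of both the remaining and the total τ²

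State that the change from 0 to 3 will not be attributed to local determinants. Either drop the country random effect or model state as random within country.

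Models 0 and 3 are in substance already planned, so the cost is SAP wording and two more fits per intervention. No new data are needed: Protocol Table S3 lists all five covariates as available at local level in all nine countries. The share reported as explained may become smaller.
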